Since the trial began, preliminary data from another randomized trial comparing cell culture-based, recombinant and egg-based SD vaccines have become available and suggest that recombinant vaccine induces higher antibody titers against both egg- and cell-grown vaccine reference viruses compared to egg-based vaccines, whereas cell culture-based vaccine does not (personal communication, [name], CDC). Data from observational vaccine effectiveness analyses comparing cell culture-based vaccine to egg-based vaccines are mixed with some analyses suggesting little to no difference in effectiveness between vaccines.^{3,4} However, it is unknown whether repeated vaccination with cell culture-based or recombinant vaccines provides additional benefit compared to first-time receipt of these vaccines or whether the improved humoral immune response to recombinant vaccine that contains three times the antigen dose of SD influenza vaccines is driven by response to recombinant antigen, higher antigen dose, or both.

Year two of this trial will examine two hypotheses. The first hypothesis is that repeated vaccination with cell culture-based or recombinant vaccines boosts antibody titers against cell-grown viruses more than first-time

vaccination with these vaccines, after receipt of egg-based SD vaccines. To address this hypothesis, participants from year one of the trial who received cell culture-based or recombinant influenza vaccines will be re-randomized to receive one of these two vaccines in year two of the trial and participants who received egg-based SD vaccines will be re-randomized to receive a cell-culture based, recombinant or egg-based SD vaccine (represented by Fluzone® Quadrivalent). The second hypothesis is that higher antigen doses, regardless of whether egg- or cell-grown, will result in higher antibody titers against cell-grown viruses. To address this hypothesis, the trial will enroll additional participants at the Kaiser Permanente Northwest site into a non-randomized vaccine arm in which participants will receive Fluzone® High-Dose influenza vaccine. Fluzone® High-Dose is an egg-based vaccine that contains four times the antigen content (60 µg of HA per strain) compared to SD influenza vaccine and is licensed for use in persons aged ≥ 65 years. In this trial, Fluzone® High-Dose will be used off-label among persons aged 18-64 years (see Rationale for Off-Label Use of Fluzone® High-Dose Among Healthcare Personnel Aged 18-64 Years).

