Study Design: Year two of the trial will be open-label and will include both randomized and non-randomized arms (Figure 3). Since the proposed trial design is a modification of the original protocol, the consent process will be repeated for all participants from year one of the trial. Participants from year one who received Flucelvax™ Quadrivalent or Flublok® Quadrivalent will be randomized 1:1 to receive Flucelvax™ Quadrivalent or Flublok® Quadrivalent in year two (Figure 3). Participants who received an egg-based SD vaccine in year one (Fluzone® Quadrivalent or Fluarix Quadrivalent) will be randomized 1:1:1 to receive Flucelvax™ Quadrivalent, Flublok® Quadrivalent, or Fluzone® Quadrivalent in year two.

Both sites may also aim to enroll additional participants to achieve a total of 150 participants per site (including participants who continue from year one plus additional newly enrolled participants) who received egg-based SD influenza vaccine during the 2018-2019 influenza season and who will be randomized 1:1:1 to receive Flucelvax™ Quadrivalent, Flublok® Quadrivalent, or Fluzone® Quadrivalent in year two. The KPNW site will also enroll up to 80 new participants for a non-randomized study arm that will receive Fluzone® High-Dose.

The study will prioritize enrollment of HCP who participated in a previous study of influenza vaccine effectiveness that was conducted at both study sites during the 2010-2011 influenza season. Stratified enrollment will be used for both randomized and non-randomized arms to ensure an even mix of age groups (18-44 years and 45-65 years) in each study arm.

Figure 3 Stratified randomization and sample size goals for groups with new enrollees per site

[figure not shown]
[figure not shown]

Figure 4 Study activity flow diagram, Year two

Consent/Screening/Enrollment:

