Participants who present with moderate to severe illness with fever and/or acute illness during the study visit will not receive study vaccine until their illness has resolved. In this case, a follow-up appointment will be made after resolution of the illness, at which time the participant will receive the vaccine.

Randomization of Participants in Year two of the Study

Study nurses administering vaccine will consult participants' study files to confirm which study vaccine participants from year one received during the first year of the study. For the purposes of randomization, newly enrolled participants into the main trial who did not participate in year one will be treated as part of the group who received FluZone® Quadrivalent or Fluarix ® Quadrivalent during year one.

Stratified block randomization will be used at each site to ensure even allocation of age groups (18-44 years and either 45-65 years) to each study arm (Figure 3). Within each age stratum:

- participants who received Flucelvax™ Quadrivalent in year one will be randomized 1:1 to receive one 0.5 mL intramuscular dose Flucelvax™ Quadrivalent or Flublok® Quadrivalent;
- participants who received Flublok® Quadrivalent in year one will be randomized 1:1 to receive one 0.5 mL intramuscular dose of Flucelvax™ Quadrivalent or Flublok® Quadrivalent; and
- participants who received FluZone® Quadrivalent or Fluarix ® Quadrivalent in year one or who were newly enrolled into the main trial will be randomized 1:1:1 to receive one 0.5 mL intramuscular dose of Flucelvax™ Quadrivalent, Flublok® Quadrivalent , or FluZone® Quadrivalent.

Randomization lists will be generated using a computerized random-number generator to select randomly permuted group blocks of six with either three in each block assigned to Flucelvax™ Quadrivalent and Flublok® Quadrivalent for those who received Flucelvax™ Quadrivalent or Flublok® Quadrivalent in year one or two in each block assigned to FluZone® Quadrivalent or Flucelvax™ Quadrivalent or Flublok® Quadrivalent for those who received FluZone® Quadrivalent in year one or are newly enrolled to the main trial in year two. The next available sequential study-number will be assigned to each enrolled participant upon study-entry.

Participants who are newly enrolled into the FluZone® High-Dose substudy will not be randomized and will all receive FluZone® High-Dose.

'Opt-In Consent for Longitudinal PBMC Collection:

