For newly enrolled participants, site investigators will extract (or abstract if necessary) data from participants' electronic medical records and state immunization registries on influenza vaccination history during the preceding ten years to include, date of receipt, vaccine product name, vaccine lot number, and route of administration (Appendix T, EMR/Chart Extraction/Abstraction Form, Year 2). Participants may be asked to sign release of medical information forms to allow access to vaccination records as needed to meet site-specific data access requirements.

For participants who were in year one of the trial, site investigators will limit extraction (or abstraction) to collecting data on influenza vaccination during the 2011-2012 and 2012-2013 influenza season.

Statistical Analysis for Year Two:

Humoral antibody responses as measured by HI (and MN, NAI and ADCC, as appropriate) at baseline (day 0) and approximately 28 days post-vaccination will be compared between participants in each study arm as outlined in Table 5; additional comparisons may be made as appropriate. Ninety-five percent confidence intervals will be calculated for relevant antibody response measures as outlined in the study endpoints at each time point (day 0 and approximately 28 days post-vaccination). Post-vaccination GMTs and MFRs at each time point post-vaccination may be compared between study arms using repeated measures mixed models with time point and vaccine as well as their interaction as independent variables; ANOVA will be used to allow for adjustment for imbalances between vaccine groups. Titers \geq seropositive thresholds at 1:40, 1:80, 1:160 and SCR may be compared with Chi Square tests. Adjustment for multiple comparisons to meet the primary objectives will be done using a Bonferroni correction approach.

Cell-mediated immune responses at baseline and approximately 7 days and 28 days will be compared between participants in each study arm. ANOVA will be used to carry out comparisons of cell-mediated immunity studies, and Bonferroni correction may be used to adjust for multiple comparisons.

All primary analyses will be conducted as intention-to-treat. All tests will be 2-tailed with a level of significance of .05.

Table 5 Planned statistical comparisons for primary objectives and endpoints in year two

Primary Objective	Comparison Group 1	Comparison Group 2

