Compare immune responses after two consecutive years of vaccination with cell-based influenza vaccine (Flucelvax™ Quadrivalent) or recombinant influenza vaccine (Flublok® Quadrivalent) versus first time receipt of these vaccines following vaccination with SD egg-based influenza vaccines.	Flucelvax™ Quadrivalent year one/year two	SD egg-based vaccine year one/Flucelvax™ Quadrivalent year two
	Flublok® Quadrivalent year one/year two	SD egg-based vaccine year one/Flublok® Quadrivalent year two
Compare immune responses after two consecutive years of vaccination with cell-based influenza vaccine (Flucelvax™ Quadrivalent), recombinant influenza vaccine (Flublok® Quadrivalent), or SD egg-based vaccine (Fluzone SD).	Flucelvax™ Quadrivalent year one/year two	SD egg-based vaccine year one/year two
	Flublok® Quadrivalent year one/year two	SD egg-based vaccine year one/year two

Compare immune responses after cell culture-based influenza vaccine (Flucelvax™ Quadrivalent) versus recombinant influenza vaccine (Flublok® Quadrivalent) at approximately 28 days after receipt of the 2019-2020 vaccines, regardless of prior vaccination status.	Flucelvax™ Quadrivalent year 2 (regardless of year one vaccine)	Flublok® Quadrivalent year 2 (regardless of year one vaccine)
Compare immune responses after first time vaccination with cell-based influenza vaccine (Flucelvax™ Quadrivalent), recombinant influenza vaccine (Flublok® Quadrivalent), or high-dose egg-based vaccine (Fluzone High-Dose) following vaccination with SD egg-based influenza vaccines to repeated vaccination with SD egg-based vaccine.	SD egg-based vaccine year one/Flucelvax™ Quadrivalent year two SD egg-based vaccine year one/Flublok® Quadrivalent year two Fluzone HD year two	SD egg-based vaccine year one/year two

SD: Standard dose; HD: High dose

Power/Sample Size Calculations:

Study sample size was determined based on available resources. An overall sample size of up to 830 with

- 90 participants each in the Flublok® Quadrivalent year one/ Flucelvax™ Quadrivalent year two group and Flublok® Quadrivalent year one/year two group
- 135 participants each in the Flucelvax™ Quadrivalent year one/year two group and Flucelvax™ Quadrivalent year one/ Flublok® Quadrivalent year two group
- 100 participants each in the SD (SD) egg-based vaccine year one/Flucelvax™ Quadrivalent year two, SD egg-based vaccine year one/Flublok® Quadrivalent year two, and SD egg-based vaccine year one/year two groups, and

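### The primary High-Dose v SD/SD contrast is non-randomised with a known site imbalance, yet the plan names no site term for titres and only a chi-square for seroconversion

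*Combined protocol and SAP*

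**What the plan says.** **The contrast is primary.** Primary Objective 4 and the last row of Table 5 compare first-time cell-based, recombinant or "high-dose egg-based vaccine (Fluzone High-Dose) following vaccination with SD egg-based influenza vaccines to repeated vaccination with SD egg-based vaccine". The Background ties the High-Dose arm to the antigen-dose hypothesis: "The second hypothesis is that higher antigen doses, regardless of whether egg- or cell-grown, will result in higher antibody titers".

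**How the two groups arise.** Under Study Design, "The KPNW site will also enroll up to 80 new participants for a non-randomized study arm that will receive" High-Dose. The randomisation section says that these participants "will not be randomized and will all receive" High-Dose. The SD/SD group is one of three arms randomised 1:1:1 among people with a prior standard-dose egg-based vaccine: "Both sites may also aim to enroll additional participants to achieve a total of 150 participants per site", counting returning and new participants together.

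**What is balanced by design.** Enrolment is stratified by age group in the non-randomised arm too. New enrollees must have had an egg-based standard-dose vaccine in 2018-19.

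**Analysis.** Under Statistical Analysis for Year Two, GMTs and MFRs may be compared with a repeated measures model on time point and "vaccine as well as their interaction as independent variables; ANOVA will be used to allow for adjustment for imbalances between vaccine groups". For binary endpoints, the seropositivity thresholds and "SCR may be compared with Chi Square tests". SCR and the GMT ratio are both listed as primary endpoints. Where the amendment is silent, methods follow the original protocol, which is not among the documents.

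**The concern.** The site imbalance follows from the design and is known before anyone is enrolled: 100% KPNW in one group, about 50% in the other. If titres or response rates differ between the sites, part of that difference appears as a High-Dose effect. Intention-to-treat gives no protection here, because the High-Dose group was not randomised. Table 5 nevertheless lists the contrast beside randomised ones without a label.

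At stake is the test of the antigen-dose hypothesis. For titres, the result would depend on whether site is later judged to be one of the unspecified imbalances. For SCR, the named test has no place for a covariate.

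**Working it through.** **Inputs from the documents.** High-Dose 80; SD/SD 100; KPNW SD/SD = 150/3 = 50, so KPNW share w = 0.5 (this assumes the 150-per-site goal is met). Alpha = 0.05/8 = 0.00625, two-sided (Table 6).

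**Inputs assumed.** Site effect and SD of log titre; the documents give neither.

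**1. Table 6.** The SD and power are not stated. A two-sample t-test at 0.05/8 reproduces N = 16, 22, 34, 69, 245 exactly with natural-log SD 0.2936 at 80% power, or 0.2615 at 90%. So Table 6 implies an SD of about 0.26 to 0.29. I also show 0.6 and 1.0 as assumptions.

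**2. Shift in the unadjusted day-28 GMT ratio.** With site ratio R and no vaccine effect, the shift is exp[(1 - w) ln R] = √R. R = 1.1 gives 1.05; R = 1.2 gives 1.10.

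**3. False positives, unadjusted.** SE = SD × √(1/80 + 1/100) = 0.15 × SD. The noncentrality is 0.5 ln R / SE. For R = 1.2 and SD 0.6 this is 0.0912/0.09 = 1.01.

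| Log SD | R = 1.1 | R = 1.2 |
|---|---|---|
| 1.0 | 0.9% | 1.7% |
| 0.6 | 1.4% | 4.2% |
| 0.26 to 0.29 (Table 6) | 5% to 6% | 23% to 34% |

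The nominal rate is 0.6%. The ranges in the last row also cover whether the SD is read as within-site or within-arm.

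**4. SCR by chi-square.** Assumed site rates of 40% (KPNW) v 30%: the shift is 0.40 - (0.5 × 0.40 + 0.5 × 0.30) = 5 points, with false positives of about 2% by simulation. Rates of 50% v 30% give 10 points and about 8%.

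**5. What is not exposed.** A constant site offset on the log scale is present at day 0 and at day 28, so it cancels in MFR and in the vaccine-by-time interaction. SCR rests mainly on a four-fold rise. A constant offset reaches it only through the condition that the post-vaccination titre be at least 40; otherwise response rates must differ by site.

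**6. Precision with a site term.** The variance of the contrast is SD² times:
- unadjusted: 1/80 + 1/100 = 0.0225
- site term, High-Dose and SD/SD only (equivalent to KPNW only): 1/80 + 1/50 = 0.0325
- site term, High-Dose plus the three prior-SD arms, with site estimated from 150 v 150: 1/80 + 1/100 + 0.25 × (1/150 + 1/150) = 0.0258

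Power for a ratio of 1.2 at 0.05/8, before any gain from the baseline covariate:

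| Log SD | Unadjusted | Site term, three prior-SD arms | High-Dose and SD/SD only |
|---|---|---|---|
| 0.2936 | 91% | 87% | 75% |
| 0.26 | 97% | 95% | 86% |
| 0.6 | 23% | 20% | 14% |

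In simulation with only a site effect present, the site-term model gave a mean ratio of 1.00 and false positives of 0.5% to 0.6%. That confirms the algebra; it says nothing about other sources of confounding.

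**The case against.** **Adjustment is already planned.** The ANOVA sentence says that adjustment will be allowed for, and site is the most obvious imbalance. This largely stands for titres: the gap is that no covariate is named, not that adjustment is excluded. A reader might infer that the plan ignores the problem; the text does not support that.

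**The chi-square is permissive.** The wording is that it may be used. True, but no adjusted or stratified SCR method is named in its place.

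**The original protocol may fill the gap.** It could name covariates or an SCR model. This cannot be excluded, although the amendment has its own statistical section. The absence can be claimed only for the amendment.

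**The size is assumed.** This stands. A reader might take 23% to 34% as the expected error rate. It needs a site ratio of 1.2 together with the small SDs implied by Table 6, and nothing in the documents supports that pairing.

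**A site term does not make the contrast randomised.** This also stands. Enrolment status and self-selection into an off-label arm are left untouched.

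**Conclusion.** The point holds as a prespecification gap for titres and as a weak choice of named method for SCR, in one primary contrast. Illustratively, an assumed site ratio of 1.1 to 1.2 multiplies the unadjusted day-28 GMT ratio by about 1.05 to 1.10. False positives are then about 1% to 4% at log SD 0.6 to 1.0, and higher at the Table 6 SDs. Assumed site SCRs of 40% v 30% shift the difference by 5 points. All of this assumes that half of SD/SD is at KPNW and that site is left out of the analysis; MFR is protected against a constant offset.

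A reader might infer that vaccine and site are inseparable. They are not: about 50 SD/SD participants should be at KPNW, and age mix and prior-season vaccine type are addressed by design. The confounding is partial. It merits a change because the imbalance is known in advance and the variables needed are already collected.

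**What to change.** For High-Dose v SD/SD, prespecify:
- a model of log day-28 titre on vaccine, site, age stratum and log baseline titre;
- logistic regression with the same terms for SCR, in place of the chi-square;
- a KPNW-only comparison (80 v about 50) as a sensitivity analysis;
- a non-randomised label on this row of Table 5, and a stated limitation that confounding by new-enrollee status and self-selection remains.

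Fitting the three prior-SD arms together with High-Dose is an option that recovers precision if vaccine effects are the same at both sites.

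The cost is SAP wording and a few model runs, with no new participants, visits or assays. At the Table 6 SDs, power for a ratio of 1.2 falls from 91-97% to 87-95% with the three prior-SD arms, or to 75-86% with High-Dose and SD/SD only, before any gain from the baseline covariate.

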- 80 participants in the Fluzone HD year two group

would provide adequate statistical power to detect a post-vaccination GMT ratio of 1.2 between comparison groups as outlined in table 5 after adjusting for up to seven comparisons using a Bonferroni correction. Table 6 provides estimated sample sizes per comparison group required for varying post-vaccination GMT ratios after adjustment for up to eight comparisons.

Table 6. Sample size calculations to detect specified post-vaccination GMT ratios between two comparison groups after adjustment for eight primary comparisons using a Bonferroni correction

GMT ratio	N per group
1.5	16

1.4	22
1.3	34
1.2	69
1.1	245

Vaccine Product:

Four vaccine products will be used during the 2019-2020 season of this trial: Fluzone® Quadrivalent, Flucelvax™ Quadrivalent, Flublok® Quadrivalent, and Fluzone Trivalent High Dose. CDC or study sites will purchase vaccine. Fluzone® Quadrivalent, Flucelvax™ Quadrivalent, and Flublok® Quadrivalent are inactivated influenza vaccines that are approved for use in adults aged ≥ 18 years in the United States. Fluzone Trivalent High Dose is an inactivated vaccine that is licensed for use in adults aged ≥ 65 years in the United States and will be used off-label in this trial. All four vaccine products will contain vaccine strains representative of the following three strains in the 2019-2020 formulation: an A/Brisbane/02/2018 (H1N1)pdm09-like virus; A/Kansas/14/2017 (H3N2)-like virus; and a B/Colorado/06/2017-like virus (B/Victoria/2/87 lineage). All quadrivalent vaccine products will also include a B/Phuket/3073/2013-like virus (B/Yamagata/16/88 lineage).

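### Holm's step-down test would give the eight primary comparisons the same error control as the planned Bonferroni correction, with equal or modestly higher power, for a one-sentence change

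*Combined protocol and SAP*

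**What the plan says.** Statistical Analysis for Year Two gives the multiplicity rule in one sentence: "Adjustment for multiple comparisons to meet the primary objectives will be done using a Bonferroni correction approach". The same section sets the overall level ("All tests will be 2-tailed with a level of significance of .05") and plans intervals without describing any adjustment: "Ninety-five percent confidence intervals will be calculated for relevant antibody response measures as outlined in the study endpoints at each time point". No step-down or other sequential version is mentioned.

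Counting the rows of Table 5 gives 2 + 2 + 1 + 3 = 8 comparisons. The title of Table 6 agrees ("after adjustment for eight primary comparisons using a Bonferroni correction"). The power sentence just above it differs ("after adjusting for up to seven comparisons using a Bonferroni correction").

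Under Power/Sample Size Calculations the plan says "Study sample size was determined based on available resources", and that the resulting groups "would provide adequate statistical power to detect a post-vaccination GMT ratio of 1.2 between comparison groups". That statement is made after the Bonferroni correction.

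**The concern.** Bonferroni holds every comparison to 0.00625, however many of the others have already been rejected. Holm orders the p-values and compares the smallest with 0.05/8, the next with 0.05/7, and so on up to 0.05/1, stopping at the first failure. It needs no assumption about how the comparisons are correlated. Whatever Bonferroni rejects, Holm also rejects.

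The sample size is fixed by resources, so the testing rule is one of the few places left to gain power. Holm gains when several comparisons are real together, and the Background gives some reason to expect that. It reports preliminary data favouring recombinant over egg-based vaccine, and it hypothesises a benefit of higher antigen dose. Five of the eight comparisons also share one comparator, the group given egg-based standard-dose (SD) vaccine in both years (SD/SD).

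A second, smaller matter is that the adjusted tests sit beside plain 95% intervals. A GMT ratio can then have an interval that excludes 1 and still fail the plan's own test, and the plan does not say how such a result will be read.

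**Working it through.** **Inputs from the documents.** Two-sided 0.05; eight comparisons; group sizes 90 and 90 (Flublok in year one), 135 and 135 (Flucelvax in year one), 100 in each of three groups (egg-based in year one), and 80 (High-Dose). The pooled Flucelvax v Flublok comparison therefore has 90 + 135 + 100 = 325 per side. Target GMT ratio 1.2, ln 1.2 = 0.1823.

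**Assumed, because not stated.** Power and the SD of log titre; normal log titres with equal SD; one titre per comparison.

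**Step 1: Table 6.** A two-sample t-test on ln titre at two-sided 0.00625, with 80% power and CV 0.30, so SD = √ln(1 + 0.30²) = 0.2936, gives 16 / 22 / 34 / 69 / 245 per group. This matches every row. It does not identify the inputs: 90% power with SD about 0.26 also fits, as does 0.05/7 with SD about 0.30.

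**Step 2: thresholds.** Bonferroni uses 0.00625 throughout. Holm uses 0.00625, 0.00714, 0.00833, 0.01, 0.0125, 0.01667, 0.025, 0.05.

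**Step 3: which comparisons are real.** The pattern closest to the Background has recombinant and High-Dose higher by a common amount, cell culture equal to egg-based, and no repeat-vaccination effect. Four comparisons are then real:
- Flublok in both years v SD/SD
- first-time Flublok v SD/SD
- High-Dose v SD/SD
- pooled Flucelvax v Flublok

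**Step 4: effect set for 80% power at 100 v 100.** The effect is (2.734 + 0.842) × √(2/100) = 0.506 SD. Bonferroni power is Φ(effect/√(1/n₁ + 1/n₂) − 2.734):
- 100 v 100: Φ(3.576 − 2.734) = 80%
- 90 v 100: Φ(3.481 − 2.734) = 77%
- 80 v 100: Φ(3.371 − 2.734) = 74%
- 325 v 325: about 100%

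The mean is about 83%. Simulating the eight correlated comparisons (200,000 trials) gives:

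| | Bonferroni | Holm |
|---|---|---|
| Mean power, four real | 82.8% | 85.4% |
| All four detected | 56% | 63% |
| Holm family-wise error, same pattern | – | 3.9% |
| Family-wise error, nothing real | 4.3% | 4.3% |

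Holm lost no Bonferroni rejection in any run.

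**Step 5: ratio 1.2 at other SDs, same four-real pattern.**

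| SD(ln) | Mean power, Bonferroni | Mean power, Holm |
|---|---|---|
| 0.294 (reproduces Table 6) | 95.2% | 96.4% |
| 0.6 | 41.2% | 43.3% |
| 1.0 | 13.8% | 14.4% |

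At 0.294, detection of all four rises from 85% to 89%, and High-Dose v SD/SD from 91.9% to 94.1%.

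**Step 6: limits of the gain.** With only High-Dose v SD/SD real, power at SD 0.294 is 91.9% v 92.0%. With all eight real in a graded pattern (smallest ratio 1.2), the weakest comparison goes from 91.9% to 98.4% at SD 0.294 and from 24% to 37% at SD 0.6.

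**Step 7: intervals.** For a comparison with 80% power, the chance that the 95% interval excludes 1 while p exceeds 0.00625 is P(1.96 < Z < 2.734) with mean 3.576, which is Φ(−0.842) − Φ(−1.616) = 0.147. The eight 95% intervals cover jointly with probability about 73%; eight 99.375% intervals cover with about 96%.

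**The case against.** The strongest reply is that this is a preference. Bonferroni is valid and prespecified, no error rate or sample size is wrong because of it, and both the power statement and Table 6 already pay its cost. It also offers one fixed threshold and directly matching simultaneous intervals, which matters when the GMT ratio is a primary endpoint. All of that stands, except that the plan states only plain 95% intervals and so does not take up the matching-interval advantage.

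Three stronger readings are tempting, and the documents support none of them.
- A reader might infer that power is being thrown away for nothing. Holm adds nothing unless at least one comparison passes 0.00625, and it gives up the simple matching interval.
- A reader might assume that nearly all eight comparisons are real, where the gain is large. The Background reports that cell-culture vaccine did not raise titres over egg-based vaccine in preliminary data. The repeat-vaccination hypothesis could add real comparisons, but it is the question under test.
- A reader might think that 99.375% intervals beside Holm tests remove the disagreement between test and interval. They do not. Every comparison that Holm adds has p above 0.00625, so its 99.375% interval includes 1. In the four-real pattern at SD 0.294, the two procedures differ in 1 − 0.933 = 6.7% of trials.

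It is also fair to say that Holm must rank a defined set of p-values. Each comparison is assessed on several strains and several primary endpoints, and High-Dose is trivalent. That gap exists equally under Bonferroni.

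**Conclusion.** The point holds as a cheap improvement, not as an error in the plan. For the same 5% family-wise error, Holm does at least as well as Bonferroni in every case and somewhat better when several comparisons are real. In the pattern closest to the Background the gain is about 1 to 3 points of mean power. The chance of detecting all four real comparisons rises by 7 points (effect set for 80% power) or about 4 points (SD that reproduces Table 6). It is about nil with one real comparison and larger with more.

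That Holm never rejects fewer is a mathematical property and rests on no assumption. The size of the gain rests on normal log titres, equal SD, full planned enrolment, one titre per comparison, and an SD and power that the plan does not state. The interval point is one of labelling: the plan needs to say which result decides primary significance.

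**What to change.** Replace the multiplicity sentence in Statistical Analysis for Year Two with: *The primary hypotheses will be tested with Holm's step-down procedure at a two-sided family-wise level of 0.05 across the eight comparisons in Table 5.* Change the count of seven in the power sentence to eight so that it agrees with Tables 5 and 6. Keep Table 6 unchanged and describe it as conservative, since Bonferroni power is a lower bound for Holm.

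Label the 95% intervals as unadjusted and state that primary significance rests on the Holm-adjusted p-values. If 99.375% intervals are also printed, say that they are Bonferroni simultaneous intervals and may include 1 for a comparison that Holm rejects. They are about 2.734/1.960 ≈ 1.4 times as wide as the 95% intervals.

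The cost is a few lines of text, settled before outcome data are analysed, with no added participants, visits or assays. The downsides are the lack of a simple matching simultaneous interval, and that multiplicity across strains and endpoints remains open and needs its own statement.
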